### **9.5 EFFICACY AND SAFETY VARIABLES**

#### **9.5.1 Efficacy Assessments**

The efficacy assessments will include the CDRS-R, CGI-S, and Clinician Global Impressions-Improvement (CGI-I). Efficacy assessments are not to be administered if the patient is not accompanied by his/her consented caregiver. The K-SADS-PL and all efficacy assessments will be conducted by experienced clinicians meeting training requirements and qualifications standards established by FRI and rater training vendor.

##### ***9.5.1.1 Primary Efficacy Assessment***

The CDRS-R ([Appendix V](#); [Poznanski and Mokros, 1996](#)) is a semi-structured, clinician-rated instrument designed for use with children and adolescents between the ages of 6-17 years and contains 17 ordinaly-scaled items that evaluate the presence and severity of symptoms commonly associated with childhood depression. The CDRS-R total score ranges from 17 to 113.

The CDRS-R will be administered separately to the patient and to the caregiver. For each item, the clinician administering the interviews will select the rating that provides the best description of the patient and will then determine the total score.

### **9.5.1.2 Secondary Efficacy Assessment**

The CGI-S ([Appendix VI](#); [Guy, 1976](#)) is a clinician-rated scale used to rate the severity of the patient's current state of mental illness compared with an MDD patient population. The patient will be rated on a scale from 1 to 7, with 1 indicating a "normal, not at all ill" and 7 indicating "among the most extremely ill patients."

### **9.5.2 Safety Assessments**

Patients must be evaluated by a physician or an appropriately trained health care professional at every visit and the evaluation must be documented. The procedures discussed below will be completed at the designated visits. Scheduled safety assessments are not to be administered if the patient is not accompanied by his/her consented caregiver.

#### **9.5.2.1 Adverse Events**

An AE is any untoward medical occurrence in a patient or clinical investigation patient administered a pharmaceutical product and which does not necessarily have to have a causal relationship with this treatment. An AE can therefore be any unfavorable and unintended sign (including an abnormal laboratory finding, for example), symptom, or disease temporally associated with the use of a medicinal product, whether or not considered related to the medicinal product (ICH-E2A).

For the purpose of data collection for this study, any untoward event that was reported from the time the patient signed the ICF until 30 days after the last dose of treatment is to be considered an AE.

Examples of AEs are as follows:

- Changes in the general condition of the patient
- Subjective symptoms offered by or elicited from the patient
- Objective signs observed by the Investigator or other study center personnel

- All diseases that occur after signing ICF, including any change in severity or frequency of preexisting disease
- All clinically relevant abnormalities in laboratory values or clinically relevant physical findings that occur during the study schedule

Please note that medical procedures scheduled prior to consenting, but occurring during the study should not be captured as AEs, but should be listed in the medical history if related to a pre-existing condition.

### **9.5.2.2 Causality Assessment**

For each AE, the Investigator must provide an assessment of causal relationship to the investigational product. The causality assessment must be recorded on the appropriate AE reporting page of the patient's eCRF. Causal relationship must be assessed by answering the following question:

Is there a reasonable possibility that the investigational product caused the event?

**Yes: There is evidence to suggest a causal relationship between the investigational product and AE, ie:**

- There is a reasonable temporal relationship between the investigational product and the event, and/or
- The event is unlikely to be attributed to underlying/concurrent disease, other investigational products, or other factors, and/or
- Positive dechallenge and/or rechallenge exist

**No: There is no evidence to suggest a causal relationship between the investigational product and AE, ie:**

- There is no reasonable temporal relationship between the investigational product and the event, or
- The patient did not take the investigational product, or
- The event is likely to be attributed to underlying/concurrent disease, other investigational products, or other factors, or
- The event is commonly occurring in the (study) population independent of investigational product exposure

### 9.5.2.3 *Severity Assessment*

The Investigator will provide an assessment of the severity of each AE by recording a severity rating on the appropriate AE reporting page of the patient's eCRF. *Severity*, which is a description of the intensity of manifestation of the AE, is distinct from *seriousness*, which implies a patient outcome or AE-required treatment measure associated with a threat to life or functionality (Section 9.5.2.4). Severity will be assessed according to the following scale:

- Mild:** A type of AE that is usually transient and may require only minimal treatment or therapeutic intervention. The event does not generally interfere with usual activities of daily living
- Moderate:** A type of AE that is usually alleviated with additional specific therapeutic intervention. The event interferes with usual activities of daily living, causing discomfort but poses no significant or permanent risk of harm to the research participant
- Severe:** A type of AE that interrupts usual activities of daily living, or significantly affects clinical status, or may require intensive therapeutic intervention

### 9.5.2.4 *Serious Adverse Events*

An SAE is any untoward medical occurrence that at any dose:

- Results in death
- Is life threatening
- Requires inpatient hospitalization or prolongation of existing hospitalization
- Results in persistent or significant disability/incapacity, or
- Is a congenital anomaly/birth defect

Important medical events that may not result in death, be life threatening, or require hospitalization may be considered serious when, based on appropriate medical judgment, they may jeopardize the patient or subject and may require medical or surgical intervention to prevent one of the outcomes listed in this definition. Examples of such medical events include allergic bronchospasm requiring intensive treatment in an emergency room or at home, blood dyscrasias or convulsions that do not result in patient hospitalization, or the development of investigational product dependency or drug abuse.

Emergency room visits that do not result in hospitalization should be evaluated for one of the other serious outcomes to determine whether they qualify as SAEs.

Preplanned hospitalizations (eg, elective procedures for preexisting conditions that did not worsen, such as cosmetic surgery and hysterectomy) are excluded from SAE reporting.

#### **9.5.2.5 Reporting Adverse Events and Serious Adverse Events**

At each visit, patients are to be queried regarding any AEs or SAEs that have occurred since the previous visit. Patients will be asked to volunteer information with a nonleading question such as, “How do you feel since your last visit?” Study center personnel will record all pertinent information in the patient’s eCRF.

In addition, any SAEs reported by the patient (or patient representative) or otherwise identified by the Investigator after the study period (ie, after 30 days post last dose) should be documented and reported.

All AEs must be recorded on the appropriate AE reporting page of the patient’s eCRF whether or not they are considered causally related to the investigational product.

For every AE, the Investigator must:

- Provide an assessment of the seriousness of the event (ie, is it an SAE?), as well as the severity and causal relationship
- Document all actions taken with regard to the investigational product
- Detail any other treatment measures taken for the AE
- Document the outcome of the AE

In addition, patients are to be reminded, as described in the ICF and in accordance with [Section 9.5.2.1](#), to notify site personnel of any AEs occurring during the 30 day post-study period. Any AEs reported by the patient (or patient representative) during this period are to be recorded in original source documents. AEs are also to be recorded in the eCRF if at least one of the following conditions is met: 1) the event meets the criteria for an SAE (see [Sections 9.5.2.4](#) and [9.5.2.6](#)), and/or 2) the event is judged by the Investigator to be potentially causally related to investigational product.

Any AEs that are ongoing at the time of the final protocol-defined study visit will be followed until the condition returns to prestudy status, has resolved or stabilized, or can be explained as being unrelated to the investigational product. If a follow-up visit is deemed necessary for appropriate safety surveillance, it will take place within 30 days of the final protocol-defined study visit.

**9.5.2.6 Immediate Reporting of Serious Adverse Events and Events of Special Interest**

FRI is required to inform worldwide regulatory authorities of SAEs that meet specific criteria. Therefore, FRI must be notified immediately regarding any SAE that occurs after informed consent is obtained.

Within 24 hours of learning of any AE that meets one of the criteria for an SAE, the study center personnel must report the event to Global Drug Safety on the SAE Form for Clinical Trials. The Study Physician may also be notified by telephone.

If, during follow-up, any nonserious AE worsens and eventually meets the criteria for an SAE, that AE should be recorded as a new SAE.

The study center must transmit the SAE Form for Clinical Trials to the SAE fax number shown below. Even if an initial report is made by telephone, the SAE Form for Clinical Trials completed with all available details must still be faxed within 24 hours of knowledge of the event at the study center.

Supplemental information should be submitted as soon as available and may include laboratory results, radiology reports, progress notes, hospital admission and emergency room notes, holding and observation notes, discharge summaries, autopsy reports, and death certificates.

The Investigator is expected to take all therapeutic measures necessary for resolution of the SAE. Any medications or procedures necessary for treatment of the SAE must be recorded on the appropriate pages of the patient's eCRF. All SAEs are to be followed by the study staff until resolution or until the SAE is deemed stable. ***FRI may contact the study center to solicit additional information or follow up on the event.***

[REDACTED]

[REDACTED]

**9.5.2.7 Reporting of Pregnancies Occurring During the Study**

Study center personnel must report every pregnancy from the time the patient signs the ICF until 30 days after the last dose of investigational product. Within 24 hours of learning of a pregnancy, the study center personnel must report the event to Global Drug Safety on the Clinical Trial Pregnancy Form and fax it to the SAE/Pregnancy fax number stated in Section 9.5.2.6, even if no AE has occurred. Pregnancies in female partners of male patients occurring during the time frame described above must also be reported.

The pregnancy must be followed to term and the outcome reported by completing a follow-up Clinical Trial Pregnancy Form. If the pregnancy is associated with an SAE (eg, if the mother is hospitalized for hemorrhage), a separate SAE Form for Clinical Trials must be filed as described in [Section 9.5.2.6](#) with the appropriate serious criterion (eg, hospitalization) indicated in addition to the Pregnancy Form.

[REDACTED]

[REDACTED]

[REDACTED]

[REDACTED]

[REDACTED]

[REDACTED]

[REDACTED]

[REDACTED]

[REDACTED]

[REDACTED]

[REDACTED]

[REDACTED]

[REDACTED]

[REDACTED]

[REDACTED]

[REDACTED]

[REDACTED]

[REDACTED]

[REDACTED]

[REDACTED]

[REDACTED]

[REDACTED]

[REDACTED]

[REDACTED]

[REDACTED]

[REDACTED]

[REDACTED]

[REDACTED]

### 9.5.3 Investigational Product Concentration Measurements

**For patients enrolled under protocol amendment #3, no PK sampling will be conducted.** For patients enrolled prior to protocol amendment #3, the following procedures should be followed:

PK blood samples will be collected from assented/consented patients to determine plasma concentrations of levomilnacipran. The blood sample will be processed, stored, and shipped as indicated in [Appendix IV](#). The population PK of levomilnacipran will be characterized using serial and sparse plasma concentration-time data. Non-compartmental analysis using the serial concentration-time data will also be performed. The plasma concentration-time data collected will provide estimates of PK parameters, eg, area under the curve (AUC), half-life, maximum plasma drug concentration, and time of maximum plasma concentration.

Sparse PK blood samples will be collected during Visits 5, 6, 7, and 8, or ET as follows:

- Visit 5, a pre-dose and at 1-4 hours post-dose
- Visit 6, 4-6 hours post-dose
- Visit 7, 6-8 hours post-dose
- Visit 8, random post-dose sample

In case of scheduling constraints, the sampling times above may be collected in a different sequence among the specified visits.

From a subset of consented patients, instead of sparse PK samples, 7 serial PK blood samples will be collected at Visit 5 (or at any 24-hour period between Visit 5 and Visit 7, inclusive) at the following time points: pre-dose (20-24 hours after the most recent dose), and 2, 4, 6, 8, 10-12, and 24-hours post-dose.

To allow for a pre-dose sampling, patients who take their daily dose in the morning will be instructed to hold their daily dose on the sampling day and take it when instructed at the study center. Patients who take their dose in the evening will be instructed to not take their dose on the evening before the pre-dose sampling visit and to bring the daily dose to the site.

PK samples will not be obtained from patients who missed investigational product dosing for 2 or more consecutive days before the sampling date.

The actual date and clock times of the reference dose (the last dose taken before the PK sample) and all blood draws will be recorded in the eCRF along with the date and time of the dose before the reference dose for each patient who undergoes PK sampling.

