#### **9.4.5 Selection and Timing of Dose for Each Patient**

Patients who meet all eligibility criteria at Screening (Visit 1) and who continue to meet all the eligibility criteria for participation in the study will be assigned a randomization number at Baseline (Visit 2) and dispensed the corresponding blister card containing capsules of double-blind investigational product for Week 1. Patients will begin dosing with double-blind capsules on the next day. Patients will be instructed to take 2 capsules orally as a single dose, once daily at approximately the same time each day (morning dosing recommended), with or without food.

Dosing may be switched from the morning to another time of day if a patient prefers or if tolerability issues arise. However, any switch must allow at least 20 hours between 2 consecutive doses.

[figure not shown]

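### Protocol 9.5.3: evening dosers told to skip a dose cannot meet the 20-24 h serial pre-dose window (minor)

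*Protocol*

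**What the plan says.** Protocol 9.5.3 gives the serial subset seven draws: "pre-dose (20-24 hours after the most recent dose), and 2, 4, 6, 8, 10-12, and 24-hours post-dose". To make a pre-dose draw possible, morning dosers hold that day's dose until told to take it at the site. For the others: "Patients who take their dose in the evening will be instructed to not take their dose on the evening before the pre-dose sampling visit". They bring the dose with them.

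Four further statements bear on the point:

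- Evening dosing is allowed (9.4.5): "Dosing may be switched from the morning to another time of day if a patient prefers or if tolerability issues arise". Morning dosing is nevertheless the recommendation there and the instruction in 9.4.5.1.
- One skipped dose does not stop sampling. The bar in 9.5.3 is higher: "PK samples will not be obtained from patients who missed investigational product dosing for 2 or more consecutive days before the sampling date".
- The serial data have a stated use in 9.5.3: "Non-compartmental analysis using the serial concentration-time data will also be performed". AUC and maximum concentration are among the example parameters.
- Sampling is closed to new patients (9.5.3): "For patients enrolled under protocol amendment #3, no PK sampling will be conducted".

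The 20-24 h window is attached only to the serial schedule. The sparse pre-dose sample at Visit 5 has no window, so it raises no conflict.

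**The concern.** A site that follows 9.5.3 to the letter for an evening doser in the serial subset produces a pre-dose sample outside the window that 9.5.3 itself sets. The profile that follows starts from a lower concentration than once-daily dosing would give, because one dose is missing. If its AUC over 24 h and its peak are pooled with the other profiles as steady-state exposure, both are too low. The readable text has no exception for evening dosers and no rule on whether such a profile counts.

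**Working it through.** **Step 1: the window itself.** Let a morning doser dose at clock hour d on the day before and be sampled at hour v. The gap is (24 − d) + v. With d = v this is 24 h. For d and v between 07:00 and 10:00 it runs from (24 − 10) + 7 = 21 h to (24 − 7) + 10 = 27 h. Morning dosers can therefore meet 20-24 h.

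**Step 2: the evening doser.** Let the usual dose be at hour e, with the dose on the evening before the visit skipped. The gap is (24 − e) + 24 + v. Since e is before midnight and v is not negative, this always exceeds 24 h. The conflict therefore does not depend on any assumed clock time.

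The documents give no clock times. Assume e = 18:00-22:00 and v = 08:00-10:00:

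- shortest: (24 − 22) + 24 + 8 = 34 h
- longest: (24 − 18) + 24 + 10 = 40 h

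**Step 3: effect on AUC over 24 h.** The documents give no half-life or absorption rate. Assume one compartment, 24-hourly dosing at steady state before the gap g, half-life 8-16 h, and absorption half-life 0-4 h. Let S(t) be the share of a single dose's total AUC that lies beyond time t. With k = ln 2/half-life and ka = ln 2/absorption half-life:

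- no absorption phase: S(t) = exp(−kt)
- first-order absorption: S(t) = [ka·exp(−kt) − k·exp(−ka·t)]/(ka − k)

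The contributions of the earlier doses add up to S(g), so

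AUC ratio to steady state = 1 − S(24) + S(g).

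At g = 24 the ratio is 1, as it should be. Two worked ends:

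- Half-life 8 h, no absorption phase, g = 34: 1 − 0.125 + 0.053 = 0.928, or 7.2% low.
- Half-life 16 h, absorption half-life 4 h, g = 40: S(24) = 4/3 × 0.3536 − 1/3 × 0.0156 = 0.466 and S(40) = 4/3 × 0.1768 − 1/3 × 0.0010 = 0.235. The ratio is 1 − 0.466 + 0.235 = 0.769, or 23.1% low.

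| Gap (h) | No absorption phase: half-life 8 / 12 / 16 h | Absorption half-life 4 h: half-life 8 / 12 / 16 h |
|---|---|---|
| 20 | 1.052 / 1.065 / 1.067 | 1.088 / 1.090 / 1.084 |
| 25 | 0.990 / 0.986 / 0.985 | 0.982 / 0.980 / 0.981 |
| 27 | 0.971 / 0.960 / 0.957 | 0.949 / 0.944 / 0.945 |
| 34 | 0.928 / 0.890 / 0.876 | 0.868 / 0.842 / 0.839 |
| 40 | 0.906 / 0.849 / 0.823 | 0.827 / 0.781 / 0.769 |
| 47 | 0.892 / 0.816 / 0.777 | 0.799 / 0.732 / 0.708 |

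Without an absorption phase the peak has the same ratio as AUC. With absorption, adding up the doses numerically gives a peak of 0.775 at the lowest corner for 40 h (16 h and 4 h), so the peak is affected about as much.

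**Step 4: effect on a reported mean.** This is the evening-doser share times the deficit. At a purely illustrative 10% share it is 0.10 × 7.2% to 0.10 × 23.1%, or 0.7-2.3%. At a share of zero it is zero.

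**Step 5: two candidate fixes.**

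- *Delete the skip and change nothing else.* The gap becomes 34 − 24 = 10 h to 40 − 24 = 16 h, again outside the window. AUC is then too high: from 1 − 0.125 + 0.250 = 1.125 (8 h, no absorption phase, g = 16) up to 1.430 (8 h, absorption half-life 4 h, g = 10).
- *Move to morning dosing some days ahead.* On the nth morning dose after the changeover the ratio is 1 − S(24n) + S(24(n − 1) + g). Take half-life 16 h and absorption half-life 4 h. For n = 4 and g = 40, S(96) = 0.0208 and S(112) = 0.0104, so AUC is 1.0% low. With g = 47 it is 1.3% low.

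**Step 6: is anyone left to sample?** Protocol amendment 3 is dated 25 March 2019 and SAP amendment 2 is dated 3 October 2019, 192 days or 27.4 weeks later. Screening of at most 5 weeks plus 8 weeks of treatment is 13 weeks. By October 2019 a remaining eligible patient would require a site that took more than about 14 weeks to bring amendment 3 into effect.

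**The case against.** The strongest reply is that this is a wording slip in a procedure that is nearly closed, and that nothing important rests on it. Much of that stands. New patients are not sampled. Evening dosers in the serial subset may not exist. The PK precision target in Protocol 9.7.6.6 is for population clearance and volume, and doses for future studies come from the updated population model (9.7.8). That model can use actual times, because the reference dose and all draws are timed, "along with the date and time of the dose before the reference dose for each patient who undergoes PK sampling". The SAP introduction places PK analysis in a separate document, Protocol Appendix IV is not in the available text, and the visit procedures in 9.5.5 are redacted. A handling rule may therefore already exist, and its absence cannot be asserted.

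Three stronger readings are tempting and should be resisted:

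- *A deficit of up to 29%.* This is the 47 h row of the table, which needs an 18:00 dose and a 17:00 visit. The 10-12 h draws would then fall at 03:00-05:00 in adolescent outpatients. With a morning start the range is 7-23%.
- *Drop every serial profile outside 20-24 h.* This would remove morning dosers at 25-27 h, whose AUC is only about 1-6% low, and keep profiles at 20 h, which are 5-9% high. The retained set would lean upward.
- *9.4.5 already covers an instructed move to morning dosing.* It describes switching away from the morning, for preference or tolerability. Its spacing condition is general ("any switch must allow at least 20 hours between 2 consecutive doses"), but a sponsor-directed switch back is not described there.

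What the reply does not remove is the contradiction itself, which lies within one section and holds at any clock time. Samples already drawn also still have to be analysed.

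**Conclusion.** The instruction is wrong as written, and the matter is minor. For evening dosers in the serial subset, the skip and the 20-24 h window cannot both be met. The gap is about 34-40 h under assumed ordinary times, and AUC over 24 h in such a profile is about 7-23% below once-daily steady state. That range rests on a one-compartment model, half-lives of 8-16 h, absorption half-lives of 0-4 h and the clock times in the working, none of which the documents give. Bias in a summary arises only if evening dosers were sampled serially and their profiles are pooled as steady state.

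A reader might infer that exposure estimates used to choose paediatric doses are biased. The documents do not support that: no stated decision uses the non-compartmental results, and the population model can take the true intervals. The efficacy and safety analyses are not affected.

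**What to change.** **Profiles already collected.** Unless the separate PK plan already does this, add one sentence to it. Serial profiles whose sampling dose followed a skipped dose, identified from the recorded dose times, are shown apart from the main non-compartmental AUC and peak summaries and stay in the population PK model. Do not extend this to every profile outside 20-24 h.

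**Any patient enrolled before amendment 3 and still to be sampled.** Replace the skip in 9.5.3 with a move to morning dosing early enough that the serial dose is at least the 4th morning dose. Respect the 20 h minimum in 9.4.5, and add a short sentence that allows this switch. Do not apply it to patients who went to evening dosing for tolerability; if one is sampled, show that profile separately as above.

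**Cost.** One sentence in the PK plan, and a small wording change in 9.5.3 only if an eligible patient remains. The price is possibly a few fewer profiles in the main non-compartmental summary, and a temporary change of dosing time for any evening doser not yet sampled.
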